14.0 Risks and Benefits

14.1 Risks of Harm:

Identify all research-related risks of harm to which the subject will be exposed for each research procedure or intervention as a result of participation in this study. Consider the risks of breach of confidentiality, psychological, legal, social, and economic risks as well as physical risks. Do not describe risks from standard care procedures; only describe risks from procedures done for research purposes

All of the research procedures described are associated with minimal risk, but there are still expected risks and potential reasons to stop data collection. For example, there is potential risk associated with the finger prick. Participants may experience some discomfort, and some bruising and/or transient pain at the site of the finger prick. In addition, there are slight risks of infection. There is also a risk of an allergic reaction, if a participant has an unknown food allergy.

14.2 Measures to Minimize Risks of Harm (Precautions, safeguards):

For each research procedure or intervention, describe all measures to minimize and/or eliminate risk of harms to subjects and study personnel

To minimize risk participants will be given specific instructions to clean the finger with an alcohol pad prior to the O3I prick. Participants will be informed they can put ice on their finger if it is sore, or to minimize potential soreness. During the consenting process participants will be informed of common signs of infection, including redness and swelling, and instructed to go the medical clinic if they have any symptoms 24 hours after the finger prick.

To minimize harm from an allergic reaction researchers will monitor participants as they drink the beverage and watch for any signs of intolerance. Medical help will be called if there are signs or symptoms of an allergic response.

14.3 Confidentiality Protections (for research records, data and/or specimens):

Describe in detail the plan to maintain confidentiality of the research data, specimens, and records throughout the study and at its conclusion (e.g., destruction, long term storage, or banking). Explain the plan for securing the data (e.g., use of passwords, encryption, secure servers, firewalls, and other appropriate methods). If data will be shared electronically with other team members/collaborators outside the institution, describe the method of transmission and safeguards to maintain confidentiality. Explain whether this study may collect information that State or Federal law requires to be reported to other officials or ethically requires action, e.g., child or spouse abuse

Records of participation in this research study may only be disclosed in accordance with state and federal law, including the Federal Privacy Act, 5 U.S.C.552a, and its implementing regulations. DD Form 2005, Privacy Act Statement - Military Health Records, contains the Privacy Act Statement for the records. A copy of DD Form 2005 can be given upon request, or you can read on-line at: <http://www.dtic.mil/whs/directives/infomgt/forms/eforms/dd2005.pdf>.

Procedures to protect the confidentiality of the data in this study include, but are not limited to assigning a unique participant ID that will be used on all data collections. All forms will be kept in a restricted access, locked cabinet for five years after the study completion. Following this time period, any documentation will be destroyed or erased. To enhance the privacy of the information, survey data will be entered directly into a USU secure database such as REDcap by the participant. Individual responses are not identified and will be password protected. After verification of the database information, paper copies of all materials containing identifiers will be shredded five years after completion of the study. Researchers will make every effort to protect your privacy and confidentiality; however, there are risks of breach of information security and information loss. All efforts will be made to keep the personal information private. Information may be shared with the USUHS Institutional Review Board. Complete confidentiality cannot be promised for military personnel, because information regarding your health may be required to be reported to appropriate medical or command authorities to ensure the proper execution of the military mission, including evaluation of fitness for duty.

14.4 Potential Benefits:

Describe any real and potential benefits of the research to the subject and any potential benefits to a specific community or society

If the individuals in the research are considered experimental subjects (per 10 USC 980), and they cannot provide their own consent, the protocol must describe the intent to directly benefit all subjects

The potential benefits include enhanced knowledge about how individual dietary habits influence the Omega-3 Index. There is also a potential benefit to performance or recovery.

14.5 Privacy for Subjects:

Describe the measures to protect subject's privacy during recruitment, the consent process, and all research activities, etc.

Participants will only express interest in the study at the brief, selection will not occur until after; therefore, nobody will know who is selected unless the participant tells others they are participating. During the study, the smoothies will be handed out at a set location close to the training facility, but not where everyone in the company can see.

Records of participation in this research study may only be disclosed in accordance with state and federal law, including the Federal Privacy Act, 5 U.S.C.552a, and its implementing regulations. DD Form 2005, Privacy Act Statement - Military Health Records, contains the Privacy Act Statement for the records. A copy of DD Form 2005 can be given upon request, or can read on-line at: <http://www.dtic.mil/whs/directives/infomgt/forms/eforms/dd2005.pdf>. During data collection no identifiable information will be collected. All data will only be recorded by participant ID number. Surveys are stored on a password protected secure USU REDcap database.

14.6 Incidental or Unexpected Findings:

Describe the plan to address incidental findings and unexpected findings about individuals from screening to the end of the subject's participation in the research. In cases where the subject could possibly benefit medically or otherwise from the information, state whether or not the

results of screening, research participation, research tests, etc., will be shared with subjects or their primary care provider. State whether the researcher is obligated or mandated to report results to appropriate military or civilian authorities and explain the potential impact on the subject

Information collected through data collection for this study consists of coded data. This information is unlikely to expose a medically-sensitive concern. If found, the Principal Investigator will notify our Medical Director and appropriate Office of Human Research contact.

Similarly, data collected is unlikely to expose findings for which a researcher would be mandated to report results to appropriate military or civilian authorities.

15.0 Study Monitoring

15.1 Your study requires either Data and Safety Monitoring Plan (DSMP) or a Data and Safety Monitoring Board (DSMB).

- DSMP
- DSMB
- Both
- Not Applicable

16.0 Reportable Events

16.1 Reportable Events: Consult with the research office at your institution to ensure requirements are met. Describe plans for reporting unexpected adverse events and unanticipated problems. Address how unexpected adverse events will be identified, who will report, how often adverse events and unanticipated problems will be reviewed to determine if any changes to the protocol or consent form are needed and the scale that will be used to grade the severity of the adverse event.

Consult with the research office at your institution to ensure requirements are met

- Describe plans for reporting expected adverse events. Identify what the expected adverse events will be for this study, describe the likelihood (frequency, severity, reversibility, short-term management and any long-term implications of each expected event)
- Describe plans for reporting unexpected adverse events and unanticipated problems. Address how unexpected adverse events will be identified, who will report, how often adverse events and unanticipated problems will be reviewed to determine if any changes to the research protocol or consent form are needed and the scale that will be used to grade the severity of the adverse event

Participation in the study should not entail any physical or mental risk beyond those described. In the event of a medical emergency while participating in the study, treatment and care will be provided. Information about procedures for providing medical care to participants is disclosed in the informed consent process with participants. Any events will be reported to USU IRB.

We do not anticipate risk of many adverse or reportable events. Some potential expected risks may include: participants that do not like the drink taste or consistency may have a food aversion. In this event, participants will be asked if there is anything different that could be done to enhance their experience (ie. make the drink colder), if there isn't anything these participants may want to drop out.

Another potential risk is that participants who physically pushed themselves really hard may not be able to tolerate food or beverage immediately after finishing PT. In this scenario, researchers will let the participant rest and recover and make sure they feel better before providing the

smoothie. We will recommend participants drink the smoothies within 30-60 minutes after finishing PT. This will allow the body time to adapt.

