Study Procedures, Data Management, and Privacy

10.1 Study Procedures:

Describe step-by-step how the study will be conducted from beginning to end

This is an 8-week protocol with baseline and post-intervention data collections including: demographics, digitized questionnaires (nutrition, physical activity and sleep), O3I (collected by finger prick) and ACFT scores. We will assess changes in O3I status, performance on, and recovery from the ACFT at two H2F training sites (Ft. Campbell and Ft. Drum), after providing omega-3 enhanced or placebo smoothies. All smoothies will be pre-made, iso-caloric and provided in similar ready to drink containers. Researchers and participants will be blinded, one staff member will not be blinded and maintain the key identifying which participants receive the placebo vs intervention. A smoothie log based on participant ID will be coded (i.e., A or B) to assist in distribution of the smoothies. Each smoothie will have a lot number that ends in A or B.

Baseline visit: To account for potential confounding factors, dietary intake assessed using the Health Eating Score (HES), daily physical activity using the Physical Activity Questionnaire (PAQ), and sleep using the Pittsburg Sleep Quality Index (PSQI) sleep questionnaire will be collected using REDCap. O3I will be collected by finger prick. A baseline ACFT will be conducted by trained Army staff (not researchers). The ACFT scores will be reported to the researchers by the participants. Participants will log into REDCap to report their ACFT score and report the Rate of Perceived Exertion (RPE), a score of 6-20 and the pain score, ranging from 0-10. This will be recorded one hour and 24 hour post ACFT.

Intervention: To ensure compliance, participants will be provided an omega-3 smoothie or placebo daily (Monday-Friday) by brigade dietitians or assigned staff immediately following training.

Post-Intervention data collection: After eight weeks of intervention O3I, questionnaires and ACFT scores will be collected again with participants reporting their RPE and pain scores following the same format as the baseline visit.

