Participants will be given a USU-approved tablet to complete a digitalized participant's questionnaire, utilizing a USU-secure web based platform such as REDCap or will be emailed an anonymous survey link. Using this link, they will access REDCap to complete the questionnaires on their laptop or phone. No personally identifiable information nor personal health information will be recorded in the questionnaires. Methods to complete the questionnaire are outlined below:

1. Use a USU-approved tablet to complete the questionnaire using the USU REDCap capabilities.
2. Use their personal phone or laptop to complete the questionnaire using the USU REDCap capabilities.
 1. Research staff will email them two options to access questionnaire via REDCap
 1. Website link with an accompanying Access Code
 2. QR code to access the electronic consent documents
 3. Paper questionnaires will be available in case there are technical issues.

10.2 Data Collection:

Describe all the data variables, information to be collected, the source of the data, and how the data will be operationally measured.

Omega-3 Index This requires a finger prick with a lancet, similar to how a person with diabetes would check their blood sugar levels. This method will be used to obtain 1-2 drops of blood that will be placed on the provided collection card and sent to OmegaQuant to determine the Omega-3 Index.

Procedures for participants The Omega-3 kit include an alcohol pad to clean the finger, a blood collection card, a lancet, gauze and bandage. Instructions are included. Researchers will be assisting with the finger pricks.

Participants are instructed to: 1. Wash their hands with warm water, hold their arm down at their side for 20 seconds. 2. Use the alcohol pad to clean the index, middle or ring finger and remove any excess liquid with the gauze. 3. Twist off the blue plastic lancet cover. Place the lancet lightly on the side of the finger. Press down firmly onto the finger until you hear a click. Allow a drop of blood to collect on the finger. Lightly squeeze if needed. Then lightly touch the drop of blood to the dotted circle on the blood collection card. Completely fill the circle with blood. 4. When finished, apply pressure to the figure with the gauze pad and apply adhesive bandage. 5. Let the blood spot dry for 15-20 minutes then fold the collection card flap and place the card in the plastic bag. 6. Dispose of all materials in the trash.

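### Section 16.1 promises to report any events, but the visible plan has no systematic way to ask about them and no route from a clinic visit back to the study

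*Combined protocol and SAP*

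**What the plan says.** The reporting commitment in 16.1 is one sentence: "Any events will be reported to USU IRB". The form's printed instruction above it asks for more: "Address how unexpected adverse events will be identified, who will report, how often adverse events and unanticipated problems will be reviewed". It also asks for a severity scale.

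The plan names its own expected events. Section 14.1 lists discomfort, bruising, pain or infection at the finger-prick site, and allergic reaction. Section 16.1 adds aversion to the drink and being unable to tolerate it straight after training.

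On detection, 14.2 says that "researchers will monitor participants as they drink the beverage and watch for any signs of intolerance" and that "Medical help will be called if there are signs or symptoms of an allergic response". Section 16.1 adds that participants who dislike the drink are asked what could be improved, and that those unwell after training rest before they receive it. For finger-prick symptoms, 14.2 says participants are "instructed to go the medical clinic if they have any symptoms 24 hours after the finger prick".

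On data collection, 10.1 describes "baseline and post-intervention data collections including: demographics, digitized questionnaires (nutrition, physical activity and sleep), O3I (collected by finger prick) and ACFT scores". Sections 10.1 and 10.2 add perceived exertion and a pain score after each fitness test.

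**The concern.** A promise to report all events is only as good as the means of learning about them. Some of the events the plan expects, infection above all, develop later and away from staff. If nobody asks, and the clinic visit is not fed back, such an event may never be known to the team, and the site could still say in good faith that everything it knew of was reported. Events not collected during the eight weeks cannot be recovered at analysis.

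Two things are at stake: the completeness of what the IRB receives, and the basis for any later statement that the smoothie was well tolerated. Tolerability is not a stated objective, but 9.6 foresees guidelines and wider demand for such foods if the results are favourable, and readers will then ask how it was assessed.

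**Working it through.** The plan states no figure on this point, so the check compares sections and adds simple counts from the schedule.

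**1. Is there an event question among the data items?** Sections 10.1 and 10.2 list demographics, Healthy Eating Score, Diet ID, physical activity, sleep quality, Omega-3 Index, fitness test scores, perceived exertion and pain score. None asks about adverse events. The closest is the pain score, but it is tied to the fitness test (one hour and 24 hours afterwards) and 9.3 treats it as a recovery outcome.

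**2. Which detection routes can be read from the text?**

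| Route | Section | What it reaches |
|---|---|---|
| Watching participants drink | 14.2 | Reactions while staff are present |
| Asking those who dislike the drink for improvements | 16.1 | Aversion, once it is apparent |
| Letting those unwell after training recover first | 16.1 | Intolerance at the handout |
| Passing incidental findings to the Medical Director | 14.6 | Concerns within the study's coded data, which hold no event item |

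None is a scheduled enquiry, and no section says what staff write down.

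**3. Is there a route from the clinic to the study?** The instruction in 14.2 ends at the clinic. No visible section asks the participant to tell the team, or provides for the team to hear of the visit.

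**4. Is the reason for leaving recorded?** Section 16.1 accepts that participants who cannot get on with the drink may drop out. Section 13.6 on withdrawal deals with what happens to the data and does not record a reason. Section 11.5 allows for 20% missing data or attrition, so departures related to tolerability could pass unrecognised among the rest.

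**5. Counts from the schedule (10.1, 12.5, 9.4).**

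- Planned handouts per participant: 5 days × 8 weeks = 40.
- Days in the period: 7 × 8 = 56. Days without a planned handout: 56 − 40 = 16.
- Finger pricks: 2 × 100 participants = up to 200, each followed by the clinic instruction.

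**6. Timing of the second finger prick.** Section 12.5 places it in week 8, and 10.1 places it after eight weeks of intervention. Either way, few or no handouts follow it. Its order relative to the second fitness test is not given, so it is not settled whether the 24-hour entry falls after it.

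**7. Does 16.1 answer its own prompt?** The reply does not state how unexpected events are identified, who reports, how often events are reviewed or which severity scale applies.

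**The case against.** The strongest reply is that this is a minimal-risk study of a fortified food with frequent contact. About 40 weekday handouts give participants ample opportunity to mention a problem, and 16.1 shows staff attending to how people feel. That stands in part. It means off-site events can reach the team, but by spontaneous report and not by design.

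A second reply also stands. The consent pages are not in the review copy, and 14.2 and 16.1 both refer to information given at consent. The monitoring selection in 15.1 cannot be read. An instruction to report clinic visits, or a monitoring plan, may exist there. The point is therefore limited to the visible plan. Even so, 16.1 is where the form asks how events are identified, and its answer is present and does not say.

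Several stronger readings are tempting and should not be drawn:

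- *Only reactions seen at the handout would be counted, and every other event missed.* Spontaneous reports at weekday contacts contradict this.
- *All symptomatic participants are sent to a clinic outside the study.* The referral covers finger-prick symptoms only, and the text does not say how the clinic relates to the study. For allergic signs, staff present call for help.
- *The plan forbids a symptom question, because "No personally identifiable information nor personal health information will be recorded in the questionnaires".* The protocol already collects pain scores and sleep items, so the sentence more plausibly concerns identifiable information.
- *The arms could not be compared.* Participants and researchers are blinded and the containers are similar. The documents show no mechanism by which capture would differ by arm.
- *The true event rate could be some stated multiple of the recorded one.* That needs a capture fraction, and the documents offer no basis for one.

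**Conclusion.** The point holds as a gap between a promise and its means. On the visible text, 16.1 undertakes to report any events, while no section provides for asking about them systematically or for a clinic visit after a finger prick to reach the team. Events away from the handout point depend on participants volunteering them, so counts are likely to be incomplete.

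The number of events lost cannot be calculated, since neither an expected event rate nor a capture rate is given. The exposure is up to 200 finger pricks and 16 days per participant without a planned handout. The conclusion assumes that the consent material and any monitoring plan under 15.1 do not already supply the missing steps. If they do, 16.1 need only refer to them. The change is one the sponsor should make. It does not threaten the analysis of the Omega-3 Index or the fitness test.

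**What to change.** Add to 10.1 and 10.2 one coded item, recorded by participant ID only and worded identically in both blinded arms: any symptom, clinic visit, or smoothie missed because of feeling unwell since last asked, with type and date. Ask it at a set handout contact, in the existing 24-hour entry after the fitness test, and in the week-8 REDCap form. Record the reason when a participant withdraws (13.6). In 14.2, ask participants to tell the study team of any clinic visit after a finger prick. Tabulate events by arm and use that table to feed the IRB report. The same edit is a convenient place to state in 16.1 who reports, how often events are reviewed and which severity scale is used, since the form asks for these.

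The change affects data capture only and alters no clinical instruction. It costs one short question on contacts and forms that already exist, plus one table. The downside is that solicited questions bring in minor complaints, so the recorded event rate will look less favourable than under passive reporting.

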17.0 Equipment/non-FDA Regulated Devices

17.1 Does the study involve the use of any unique non-medical devices/equipment?

Yes No

18.0 FDA-Regulated Products

18.1 Will any drugs, dietary supplements, biologics, or devices be utilized in this study?

- Drugs
- Dietary Supplements
- Biologics
- Devices
- N/A

18.5 Sponsor (organization/institution/company):

N/A

If applicable, provide sponsor contact information:

19.0 Research Registration Requirements

19.1 ClinicalTrials.gov Registration:

- Registration is not required
- Registration pending
- Registration complete

19.2 Defense Technical Information Center Registration (Optional):

- Registration is not required
- Registration pending
- Registration complete

